7.3. Clinical Laboratory Assessments

7.3.1. Hematology

Hematology parameters will include a complete blood count: white blood cells, red blood cells, hemoglobin, hematocrit, platelets, neutrophils, lymphocytes, monocytes, eosinophils, basophils and bands (if reported). See time points specified in the Schedule of Assessments ([Appendix 1](#)). All assessments will be performed by the local laboratory.

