7.3.3. Creatinine Clearance

Creatinine clearance will be calculated using either the Cockcroft-Gault method OR as measured by 24 hour urine collection ([Appendix 3](#)). See time points specified in the Schedule of Assessments ([Appendix 1](#)).

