7.5. Efficacy Assessments

Efficacy assessments will be performed every four weeks after the initiation of study treatment. Response assessments will be performed every four weeks and will be based upon the IMWG Response Criteria ([Rajkumar 2011](#), refer to [Appendix 7](#)). In Phase 1 assessments will be performed locally, in Phase 2b assessments will be performed by a central laboratory.

All screening and Cycle 1 Day 1 efficacy assessments will include quantitative immunoglobulins, serum and urine electrophoresis, serum and urine immunofixation, and serum free light chain assay.

After Cycle 1 Day 1 assessment, SPEP and UPEP (if measureable), and other parameters, as applicable, according to the IMWG response criteria will be measured and followed.

At the Investigator's discretion additional evaluations may be performed according to standard of care but they are not to be used for response assessment.

If at any time CR is suspected, all assessment including quantitative immunoglobulins, serum protein electrophoresis and immunofixation, urine protein electrophoresis and immunofixation, serum free light chain, radiographic imaging (if applicable) and bone marrow biopsy (see [Section 7.5.7](#)) must be performed as per the IMWG response assessment guidelines.

Any suspected case of disease progression should be reported to the Sponsor within 24 hours of awareness. If disease progression is suspected solely based on the results of a single examination

or a single laboratory parameter (eg, SPEP or UPEP), this finding should be confirmed by a subsequent evaluation within no more than 4 weeks from the first finding. Additional assessments should be performed at the discretion of the treating physician to confirm progressive disease if indicated (eg, radiographic imaging).

In general, subjects should continue study treatment until progression is confirmed by a serial examination within 4 weeks from the first finding and confirmation by the IRC (Phase 2b). When disease progression has been confirmed (by the IRC for Phase 2b), study treatment should be withheld. Following confirmed disease progression, subjects should continue to adhere to all other study-related procedures. Whenever possible, subsequent anti-cancer therapy should be withheld until confirmed disease progression by the IRC for Phase 2b.

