7.5.7. Bone Marrow Aspirate and Biopsy

A unilateral bone marrow aspirate and biopsy will be obtained at Screening and submitted to a local laboratory to evaluate for morphology and document bone marrow involvement. Subjects who have had a bone marrow biopsy within 90 days of first administration of study treatment may use those bone marrow results in lieu of the baseline bone marrow biopsy required for the study, however, the bone marrow aspirate will be required within 28 days of first administration of study treatment.

Phase 1 Only: In addition, the screening bone marrow sample should have fluorescence in-situ hybridization (FISH) analysis performed locally. The analysis should include at a minimum assessment of del 17p13, t(4;14), t(11;14), t(14;16), and 1q21 (copy number) status, and should preferably also include 13q14 status ([NCCN, version 4 2015](#)). FISH analysis should preferably be performed on samples that have been enriched for plasma cells (PCs). If the FISH analysis has been performed within 90 days prior to the first administration of study treatment and includes all probes, it does not need to be repeated. Any probes not analyzed per protocol within 90 days of first administration of study treatment should be assessed during screening.

Testing will be performed at the study center's local laboratory or other clinical laboratory listed on the Investigator's Form FDA 1572. De-identified copies of all FISH results must be provided to the Sponsor.

If the subject's physical examination findings, laboratory evaluations, and radiographic evaluations suggest that CR has been achieved, an additional bone marrow aspirate and biopsy

should be obtained to confirm the CR. Bone marrow for confirmation of CR should include staining for CD138 and κ/λ mono-clonality by immunohistochemistry (IHC) or immunofluorescence and will be assessed locally.

Additional samples of bone marrow aspirate (6 mL) will be collected for biomarkers and other exploratory evaluations and submitted to a central lab at Screening and, if performed, at the time of CR and following confirmed PD (may be done at EOT or prior to a new anti-cancer therapy) (Section 7.6.2.1).

Phase 2b: FISH will be performed by central laboratory using the bone marrow aspirate collected at Screening.

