7.6.2. Biomarkers

7.6.2.1. Genetic and Molecular Prognostic Markers

Cytokines, chemokines, bone metabolism biomarkers, and exploratory investigations of predictive biomarkers and mechanisms of resistance will be tested in blood and bone marrow. Serum CTX will be collected at Screening. Samples will be collected on Day 1 of Cycle 1, and on Day 1 of every even Cycle, Suspected Disease Progression and EOT, and submitted to a central lab (refer to [Appendix 1](#)). Testing will include (T/B/NK immunophenotyping, serum CTX) and other secreted proteins. Serum CTX collection will require 12 hour fasting prior to collection. Testing will be performed at a central laboratory. Samples will be collected from all subjects.

Samples may be tested to evaluate potential biomarkers related to disease response and investigate potential mechanisms of treatment resistance. These samples may be characterized by technologies such as gene expression profiling, targeted sequencing for genomic alterations, and intracellular signaling pathway analysis. Inhibition of BTK and other related kinases may also be explored. These efforts may identify genes and pathways associated with primary or later development of resistance to ibrutinib and potentially identify biomarkers that could assist with future development of this compound. Pharmacodynamic assays, (ie, BTK occupancy) may be performed to correlate results of biomarker assessments to the physiological effects of ibrutinib.

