- ^r After disease progression, subjects will be contacted to assess survival status approximately every 12 weeks (± 14 days). After ibrutinib treatment is discontinued all information on first subsequent anti-cancer therapy will be collected to include: start date and indication for initiation of subsequent anti-cancer therapy.
- ^s Hematology (WBC, RBC, Hgb, Hct, platelet count, neutrophils, lymphocytes, monocytes, eosinophils, basophils and bands if reported). C1D1 testing not required if done within 48 hours prior to the first dose of study drug. All assessments will be performed by the local laboratory.
- ^t Chemistry (sodium, potassium, chloride, BUN/urea, creatinine, glucose, calcium, total protein, albumin, AST, ALT, alkaline phosphatase, total bilirubin, LDH, phosphate, and uric acid, and magnesium). C1D1 testing not required if done within 48 hours prior to the first dose of study drug. All assessments will be performed by the local laboratory.
- ^u Creatinine clearance is only required during Screening.
- ^v Must be done in accordance with Celgene POMALYST REMS™, RevAid®, or global Pregnancy Prevention Program (PPP) guidelines for females of childbearing potential (FCBP) only. Serum or urine depending on site standard method. If positive at Screening Visit, the subject is not eligible. A FCBP is a female who: 1) has achieved menarche at some point; or 2) has not undergone a hysterectomy or bilateral oophorectomy; or 3) has not been naturally postmenopausal (amenorrhea following cancer therapy does not rule out childbearing potential) for at least 24 consecutive months (i.e., has had menses at any time in the preceding 24 consecutive months). Pregnancy tests must occur within 10–14 days and again within 24 hours prior to initiation of Cycle 1 of pomalidomide. A FCBP with regular or no menstruation must have a pregnancy test weekly for the first 28 days and then every 28 days while on pomalidomide therapy (including breaks in therapy); at discontinuation of pomalidomide and at Day 28 post the last dose of pomalidomide. A FCBP with irregular menstruation must have a pregnancy test weekly for the first 28 days and then every 14 days while on pomalidomide therapy (including breaks in therapy), at discontinuation of pomalidomide and at Day 14 and Day 28 following the last dose of pomalidomide. To allow for drug delivery in the US, pregnancy testing can be done on Days 22-28 of each cycle.

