5 SAFETY ASSESSMENTS

Safety data will be summarized for safety population unless otherwise indicated. Table 3 summarizes the safety analyses to be carried out. AEs will be coded in accordance with the Medical Dictionary for Regulatory Activities (MedDRA). Severity of AEs were graded by the investigator according to the NCI Common Terminology Criteria for Adverse Events (NCI-CTCAE) v4.03. A listing will be provided to indicate dose-limiting toxicity (DLT).

In general, the treatment-emergent period is defined as the period from the date of the first dose of study treatment up to 30 days after the date of the last dose of study treatment or the day before initiation of subsequent anticancer therapy, whichever comes first. Treatment emergent AEs are those events that occur or worsen during the treatment-emergent period or that are related to the study treatment or events with a complete missing onset date but with a resolution date during the treatment phase.

All laboratory values will be converted to and reported as international standard (SI) units. In general, only data from the central laboratory will be summarized and analyzed. Laboratory parameters will be graded using the NCI CTCAE v4.03.

Table 3: Summary of Safety Assessments

Assessment Type	Definition	Analysis Methods
AE	TEAEs, SAEs, non-serious TEAE, grade 3 or worse TEAEs, related TEAEs, TEAEs leading to treatment discontinuation, TEAEs leading to dose reduction, TEAEs leading to death, protocol- defined events of special interest and other safety observations	Descriptive summary statistics and/or listings
Lab	Worst post-baseline toxicity grade for selected CTCAE gradable hematology and chemistry. Abnormalities in creatinine clearance, uric acid, and liver function	Descriptive summary statistics and/or listings
Vital Signs and other Observations Related to Safety	SBP, DBP, weight, heart rate, new or worsened eye-related symptoms	Descriptive summary statistics and/or listings
Dose Limiting Toxicity (DLT)	DLT	Listing

TEAE: treatment-emergent adverse event; SAE= serious adverse event; SBP: systolic blood pressure; DBP: diastolic blood pressure; CTCAE= Common Terminology Criteria for Adverse Events.

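### The SAP's default of central-laboratory data conflicts with its own Phase 1 laboratory summaries, which rest on tests the protocol assigns to local laboratories

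*SAP*

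**What the plan says.** SAP section 5 has laboratory values converted to SI units and graded by NCI CTCAE v4.03, and sets the data source: "In general, only data from the central laboratory will be summarized and analyzed". The Lab row of Table 3, in the same section, lists what is to be summarized: "Worst post-baseline toxicity grade for selected CTCAE gradable hematology and chemistry. Abnormalities in creatinine clearance, uric acid, and liver function".

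Protocol 7.3.1 says of hematology: "All assessments will be performed by the local laboratory". The same sentence closes 7.3.2 (serum chemistry) and appears in footnotes s and t of the Schedule of Assessments. None of these places distinguishes Phase 1 from Phase 2b.

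For renal function, Protocol 7.3.3 reads: "Creatinine clearance will be calculated using either the Cockcroft-Gault method OR as measured by 24 hour urine collection". It names no laboratory. Footnote u of the Schedule adds: "Creatinine clearance is only required during Screening".

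For the efficacy tests, Protocol 7.5 states: "In Phase 1 assessments will be performed locally, in Phase 2b assessments will be performed by a central laboratory".

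**The concern.** The rule and the table it governs do not fit together. The rule admits central results by default, while the table asks for summaries of tests that the protocol runs locally. An analyst who follows the rule has nothing to tabulate. One who fills the table sets the rule aside without any stated exception.

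Safety and tolerability is a primary Phase 1 objective, and the worst-grade laboratory summary is part of how the plan describes it. Some laboratory findings are protected whatever happens: the SAP lists DLTs, and Protocol 7.1.6 has abnormalities that the investigator considers clinically significant recorded as adverse events. What depends on the source rule is the systematic summary of graded abnormalities that the investigator did not flag, and showing those is the main purpose of a worst-grade table.

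**Working it through.** The plan states no figure on this point, so there is none to reproduce. The check sets the two documents side by side.

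**Step 1. Trace each Table 3 Lab item to its test and laboratory.** The SAP does not define liver function; I take it to mean AST, ALT, alkaline phosphatase and total bilirubin.

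| Table 3 Lab item | Underlying test in the protocol | Laboratory named for Phase 1 |
|---|---|---|
| Hematology, worst grade | Complete blood count, 7.3.1 | Local |
| Chemistry, worst grade | Serum chemistry panel, 7.3.2 | Local |
| Uric acid | In the 7.3.2 panel | Local |
| Liver function | In the 7.3.2 panel | Local |
| Creatinine clearance | 7.3.3 and Appendix 3 | None named |

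Expressly local: 4 of 5. Central source named: 0 of 5. The three chemistry entries share one panel, so the independent support is two panels, both local, plus creatinine clearance.

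**Step 2. Creatinine clearance.** By Cockcroft-Gault (Appendix 3) it is computed from serum creatinine, which belongs to the local chemistry panel. The alternative, a 24-hour urine collection, has no laboratory assigned. Because the measurement is required only at Screening, a later value would have to be calculated from local serum creatinine unless a site repeated the measurement. That is an inference; neither document says it.

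**Step 3. Look for any other central data in Phase 1.**
- The remaining clinical laboratory subsections do not supply any. Section 7.3 has seven (7.3.1 to 7.3.7). Five name a laboratory (7.3.1, 7.3.2, 7.3.4, 7.3.5 and 7.3.6), and all five name the local one. Sections 7.3.3 and 7.3.7 name none.
- Efficacy tests become central only in Phase 2b, which SAP section 6 says was not initiated.
- The samples expressly sent to a central laboratory in Phase 1 are biomarker samples. Protocol 7.5.7 says additional marrow aspirate "will be collected for biomarkers and other exploratory evaluations and submitted to a central lab at Screening" and at later points, and 7.6.2.1 says of the biomarker samples: "Testing will be performed at a central laboratory". SAP sections 1 and 6 cancel biomarker analysis.

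**Step 4. See whether another clause resolves the conflict.** SAP section 1 gives the SAP's analysis methods precedence over the protocol's. Precedence cannot create central results for samples that were tested locally. SAP section 6 lists three changes to the planned analysis, and a change of laboratory source is not one of them.

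**Result.** Taken at its word, the default leaves no protocol-planned data for the Table 3 Lab row.

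**The case against.** The best defence is that the sentence opens with a qualifier, so it is a default that admits exceptions, and that Table 3, being specific, should prevail over it. Protocol 10.6 points the same way: hematology and serum chemistry are to be summarized separately, all laboratory values graded, and the worst grade tabulated. SAP section 6 does not drop those summaries. Nor are there two competing datasets to choose between, so no selective choice of source can bias a result. On this view the sentence is unadapted wording that no competent analyst would follow.

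Much of this stands. The intent is fairly clear, data loss is not certain, and the weight of the point is small. The conflict itself remains. No exception is named, and the exception needed would cover essentially the whole Lab row, so the default applies to none of the summaries it governs. Protocol 10.6 cannot formally rescue it, because the SAP claims precedence where the two differ.

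Two further objections are fair in part. Counting five items makes the evidence look broader than two panels and one derived quantity, but the answer is the same on either count. It can also be said that changing one word from central to local would be enough, and that a reference-range clause is an extra. The one-word change would remove the contradiction. However, some CTCAE grades depend on the laboratory's normal limits, so once local results are the source, the plan should say whose limits apply.

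**Conclusion.** The concern holds. The stated source rule is wrong for Phase 1, the only part the SAP covers. None of the five Table 3 Lab items has a central source named in the protocol, and four are assigned to local laboratories.

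Severity is minor. The effect is confined to descriptive safety summaries in the 11 treated subjects. Protocol 10.6 plans no formal testing of safety data, and no error rate, estimate of effect or dose decision depends on the sentence.

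The conclusion assumes that testing followed the protocol. If hematology and chemistry were in fact also run centrally in Phase 1, the documents do not say so, and the SAP would need to state it.

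**What to change.** Replace the source sentence in SAP section 5 with wording such as:

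> Phase 1 hematology and serum chemistry results, and creatinine clearance measured locally or calculated from local serum creatinine, come from local laboratories. These local results will be converted to SI units, graded by NCI CTCAE v4.03 where gradable, with local reference ranges applied where the grade depends on them, and summarized.

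If creatinine clearance from 24-hour urine was tested anywhere other than the site's laboratory, the sentence should say where, since the protocol does not.

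The cost is one sentence. It uses results the protocol already collects and needs no new data. The only added work is reconciling units and reference ranges across sites, which is small with 11 subjects.

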8.4.1. Response Follow-up

Subjects who discontinue the study for reasons other than PD will be followed every 4 weeks (± 3 days) until PD. In Phase 2b, PD must be confirmed by the IRC. During this period, evaluations used for response assessment (ie labs, radiographic imaging, bone marrow biopsy) will be done per Investigator discretion.

- PRO assessments (Phase 2b only) – preferable to be performed prior to any assessments
- Collect blood samples for the following laboratory tests:
 - o Hematology
 - o Serum chemistry
 - o Quantitative immunoglobulins (IgA, IgG and IgM and if clinically indicated, IgD or IgE)
 - o Efficacy Assessments as applicable per [Section 7.5](#)
- Survival status and new anti-cancer therapy
- Investigator response assessment

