The verbatim terms used in the eCRF by Investigators to identify AEs will be coded using the Medical Dictionary for Regulatory Activities (MedDRA) and graded according to [NCI CTCAE version 4.03](#). Treatment-emergent adverse events are those AEs occurring after the first dose of study treatment and within 30 days following the last dose of study treatment (ibrutinib, pomalidomide, or dexamethasone, whichever occurs later), but before first dose date of subsequent anti-cancer therapy, whichever occurs first; any AE that is considered study drug-related regardless of the start date of the event; or any AE that is present at baseline but worsens after the first administration of study treatment in severity or is subsequently considered drug-related by the Investigator.

All TEAEs will be included in the analysis. The number and percent of subjects with TEAEs will be summarized by system organ class and preferred term. Drug related AEs, SAEs, Grade ≥ 3 AEs, AEs leading to study treatment discontinuation, dose modification, or death, and events of special interest will be summarized and listed.

Clinical Laboratory Tests

Laboratory tests will be summarized separately for hematology and serum chemistry. All laboratory values will be graded using the [NCI CTCAE \(version 4.03\)](#). The worst toxicity grade during the study will be tabulated.

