11.2.2. Adverse Event Reporting Procedures

11.2.2.1. All Adverse Events

All subjects who receive at least one dose of study drug(s) will be considered evaluable for safety assessments. All AEs whether serious or non-serious, will be documented from the time signed and dated ICF is obtained until 30 days following the last dose of study drug. All SAEs will be reported to the Sponsor Drug Safety via an SAE reporting form and will be recorded in

the eCRF from the time of ICF signing. Non-serious AEs will be recorded in the source documents from the time of ICF signing and will be recorded in the eCRF from the first dose of study drug(s).

Serious adverse events occurring more than 30 days following the last dose of study drug should also be reported if considered related to any of the study drugs. Resolution information after 30 days should be provided.

Progressive disease should NOT be reported as an AE, but instead symptoms/clinical signs of disease progression may be reported (See [Section 11.1.1](#)).

All AEs, regardless of seriousness, severity, or presumed relationship to study drug, must be recorded using medical terminology in the source document. All records will need to capture the details of the duration and the severity of each episode, the action taken with respect to the study drug, Investigator's evaluation of its relationship to the study drug, and the event outcome. Whenever possible, diagnoses should be given when signs and symptoms are due to a common etiology (e.g., cough, runny nose, sneezing, sore throat, and head congestion should be reported as "upper respiratory infection"). Investigators must record in the eCRF their opinion concerning the relationship of the AE to study therapy. All measures required for AE management must be recorded in the source document and reported according to Sponsor instructions.

All deaths should be reported with the primary cause of death as the AE term, as death is typically the outcome of the event, not the event itself. Autopsy and postmortem reports must be forwarded to the Sponsor, or designee, as outlined above, if allowed per local regulatory guidelines.

If a death occurs within 30 days after the last dose of study drug, the death must be reported to the Sponsor as a SAE.

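### The SAP's worst-grade laboratory summary has no end date, so values drawn off study drug can set the grade, and the laboratory and TEAE tables can cover different periods

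*SAP*

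**What the plan says.** - **Laboratory summary.** SAP section 5, Table 3, Lab row: "Worst post-baseline toxicity grade for selected CTCAE gradable hematology and chemistry". The start is fixed by baseline; no end is given. Protocol 10.6 has the same open scope: "The worst toxicity grade during the study will be tabulated".
- **Treatment-emergent period.** SAP section 5 runs it from first dose "up to 30 days after the date of the last dose of study treatment". It closes earlier, on the eve of any new anticancer therapy. The next sentence uses it to define TEAEs. TEAEs also include events "or that are related to the study treatment or events with a complete missing onset date" (the latter if they resolved during treatment).
- **AE collection.** Under protocol 11.2.2.1, AEs "will be documented from the time signed and dated ICF is obtained until 30 days following the last dose of study drug". After that, the section asks only for serious events judged related.
- **Laboratory sampling off drug.** Protocol 8.4.1: "Subjects who discontinue the study for reasons other than PD will be followed every 4 weeks", until progression. The section lists hematology and serum chemistry, and Appendix 1 marks both in the Response Follow-up column.
- **Data in the analysis.** SAP 1.4 places the final analysis after all Phase 1 subjects have exited. SAP section 1 gives 11 treated subjects.
- **Laboratory source.** SAP section 5 says that, in general, only central-laboratory results are summarized. Protocol 7.3.1 and 7.3.2 have hematology and chemistry done locally.

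**The concern.** A worst-grade table in a Phase 1 report is normally read as toxicity of the regimen. With no end date, a value drawn weeks or months after the last dose counts as much as one drawn on treatment. Protocol section 1.1 lists anemia, thrombocytopenia, neutropenia, hypercalcemia and renal insufficiency among the effects of myeloma itself. Follow-up runs up to progression, so it reaches the time when these may return. The AE tables largely exclude that time, and nothing in the output would tell a reader that the two sets of tables cover different periods. Safety and tolerability is one of the two primary Phase 1 objectives, so the table matters even though nothing is tested.

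**Working it through.** The plan states no figure to reproduce. The check compares windows and does visit arithmetic.

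**1. Is the laboratory window closed anywhere?** SAP section 5 and Table 3, and protocol 10.6, contain no sentence that ends it or applies the treatment-emergent period to laboratory values. Elsewhere the SAP does set such limits: Table 2 stops ORR and CBR at subsequent therapy, and TEAEs have their period.

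**2. Do scheduled samples fall outside the 30-day period?**
- End-of-Treatment visit (protocol 8.3.12): 30 ± 7 days after last dose, so days 23 to 37. A sample within its permitted window can lie up to 37 − 30 = 7 days past the cut.
- First Response Follow-up visit: 28 ± 3 days, counted from End-of-Treatment (assumption). Earliest 23 + 25 = day 48; latest 37 + 31 = day 68. The whole range lies beyond day 30, as do all later visits.

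**3. Which way can the table move?** Let W be the values inside the treatment-emergent period and L the later ones. The reported grade is max(W ∪ L) ≥ max(W). Off-drug values can raise the worst grade or leave it; they cannot lower it.

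**4. How much can it move?** One affected subject among 11 changes a cell by 1/11 = 9.1 percentage points. The number affected is not in the documents.

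**5. How many scheduled samples could be off drug?** This is an illustration only. Take a subject who stops after two cycles without progression and has k follow-up visits. From Appendix 1, post-baseline on-treatment hematology falls on C1D8, C1D15, C1D22, C2D1 and C2D15 (5 draws) and chemistry on C2D1 (1 draw). Each has one End-of-Treatment draw.

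| k | Hematology, k/(6 + k) | Chemistry, k/(2 + k) |
|---|---|---|
| 1 | 1/7 = 14% | 1/3 = 33% |
| 6 | 6/12 = 50% | 6/8 = 75% |

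These are shares of draws, not the chance that the worst grade is an off-drug one.

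**6. Which laboratory?** Protocol 7.3.1, 7.3.2 and the Appendix 1 footnotes make hematology and chemistry local. Applied literally, the SAP's central-only sentence would leave the table largely empty, on drug and off.

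**The case against.** **The period may have been meant for all safety data.** It is introduced as a general definition ahead of Table 3, so an author could have intended it for laboratory values. That is possible, but no sentence says so, and the protocol's wording points the other way. If it was the intent, stating it costs nothing.

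**An open window is a legitimate choice.** It carries out protocol 10.6 faithfully, catches delayed toxicity, and a CTCAE grade attributes nothing to study drug. This stands in part: the SAP does not contradict the protocol. The unstated mismatch with the TEAE period remains, and a listing of later values would still show delayed toxicity.

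**Few subjects are exposed.** Response Follow-up covers only those who stopped for reasons other than progression and ends at progression. Section 8.4.1 leaves evaluations used for response assessment, laboratory tests among them, to the investigator. Continuation after new therapy is stated only for Phase 2b. All of this stands, and it is why no size can be given. Ending at progression does not remove the problem, however: the Suspected PD visit (protocol 8.3.11) can take place at any time during the study and itself draws hematology and chemistry.

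**The worst grade may occur on drug anyway.** Protocol 1.3.2 cites Grade 3-4 neutropenia of 41% and 48% with pomalidomide and dexamethasone. This is fair for neutrophils, where an off-drug value would often change nothing. A reader might infer from step 5 that half or more of the tabulated grades are off-drug; the documents do not support that.

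**The AE cut is not a clean 30 days.** Correct. It comes earlier if new therapy starts, and related events count at any date. A reader might infer that the AE tables stop at day 30; they do not strictly do so, although later collection is narrow.

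**Conclusion.** The point holds as a flaw in a stated rule. Followed literally, the Lab row lets off-drug values set the worst grade for subjects who stopped without progression, and the laboratory and TEAE tables can then cover different periods. Any effect is toward more apparent toxicity. Its size is unknown: 9.1 percentage points per affected subject, with the number of such subjects not given. It rests on follow-up samples having been taken as scheduled for at least one subject, and on the treatment-emergent period not being meant for laboratory values.

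A reader might infer that the primary objective or the dose conclusion is compromised. The documents do not support that. DLTs are judged on Cycle 1 and the pre-dose assessments of Cycle 2 Day 1 (protocol 5.1), and the MTD/MAD follows from them. Laboratory abnormalities that the investigator considers clinically significant are also recorded as AEs up to 30 days after the last dose (protocol 7.1.6). The laboratory output is descriptive, with no formal test. The point is worth correcting before the table is programmed, but goes no further than the interpretation of that table.

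**What to change.** 1. In the Lab row of SAP Table 3, change the definition to: worst post-baseline grade within the treatment-emergent period defined above. Apply the same period to the other abnormalities named in that row.
2. State whether an End-of-Treatment sample taken inside its ± 7-day window (up to day 37) but before new therapy is included.
3. Put later values in a listing, flagged as off treatment.
4. In the same section, reconcile the central-laboratory restriction with the local hematology and chemistry of protocol 7.3.1 and 7.3.2. Without this, the date limit would be applied to a largely empty table.

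The cost is a few phrases in SAP section 5, a date filter in the laboratory program and one listing. No new data are needed.
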